## Adjuvant Radiotherapy for Resected Hepatocellular Carcinoma With MVI

NCT 04891874 2015-8-1 **Objectives:** Marginal resection frequently occurred in hepatectomy for hepatocellular carcinoma (HCC), which led to increased local recurrence, especially among patients with microvascular invasion (MVI). Stereotactic body radiotherapy (SBRT) shows effective in tumor controlling, while limited research reported the efficacy of SBRT as adjuvant setting for HCC. This prospective randomized controlled study aims to investigate the efficacy of SBRT as adjuvant setting for HCC as adjuvant setting for HCC patients with MVI and positive resection margin.

**Design:** This is a single center, prospective, randomized controlled clinical trial measuring the efficacy of SBRT as adjuvant therapy for early HCC with MVI after surgery.

**Methods:** Participants with HCC and MVI receiving marginal resection were randomly assigned to postoperative adjuvant SBRT group or surgery alone (SA) group. Patients in SBRT group received SBRT targeting on the resection marginal parenchyma one month after surgery. The disease-free survival (DFS) and overall survival (OS) were compared between the groups and the adverse events (AE) in the SBRT group were recorded.

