## Protocol

- 1. Adult patients diagnosed with hepatocellular carcinoma, suitable for partial hepatectomy were considered as potential candidates while the patients were referred to hospital (n=263).
- 2. In-hospital examination includes physical status, liver function and tumor stage. Patients with Child-Pugh A liver function, ECOG physical status 0/1, and BCLC stage 0/A were good candidates for surgical resection. These patients would be put forward to surgery and waiting for the postoperative pathological examination. Marginal resection was applied while tumor was adjacent to major vasculature or severe cirrhosis existed. We routinely mark the unsafe resection margin with silver clips for potential adjuvant postoperative therapy.
- 3. Once pathological examination proved micro-vascular invasion in paratumoral tissue, which meant a higher incidence of early recurrence for the patient, the patient would be considered as a candidate for enrollment.
- 4. The protocol and detail of the trial would be clearly explained to the patient and the written informed consent were collected if the patient agreed to be enrolled.
- 5. Randomization: Randomization was carried out using the random sequence method of EXCEL, keeping a 1:1 ratio in groups. Two nurses on daily duty accomplished the randomization and allocation work. Participants in SBRT group would be sent to a separate team of radiologists who carried out the radiotherapy and follow-up survey (n=76).
- 6. Concealment: Concealment was not attached in the SBRT group and blinding was not applied due to the SBRT procedure.
- 7. Surgery: The conventional open partial hepatectomy was applied in this study. After removal of the tumor, silver clips were imbedded to mark where resection

margin was narrow and absent. The marginal liver resection was defined as the minimal distance from tumor edge to the cut surface <5mm, regardless of the margin was positive or not.

- 8. Radiotherapy: SBRT was delivered by the CyberKnife® system (Accuracy Inc., Sunnyvale, CA, USA) with tumor tracking devices. All the patients received fiducial marker implantation in operation for the tumor tracking technique.
- 9. Follow-up: All the participants received follow-up every 3 months until recurrence or censored.

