## Statistical analysis

The comparison of clinical parameters between the two groups were conducted by the Student's t test, the Mann Whitney U-test, the Chi-square test or Fisher's exact test, relying on the variables as appropriate. The DFS and OS were determined by the Kaplan-Meier method which was generated by the log-rank test. The univariate and multivariate analyses were conducted to identify the independent risk factors of DFS and OS in the entire group of BCLC 0/A patients receiving operation in the recruitment period. Variables with P < 0.1 on univariable analysis were subjected to the multivariable Cox regression model using a forward stepwise variable selection. The statistical significance level was set at P < 0.05 in all the analyses.

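### Adverse events are to be recorded in the SBRT group only, so the randomized difference in non-fatal adverse events cannot be estimated if the plan is followed as written

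*Protocol*

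**What the plan says.** The Methods paragraph of the Protocol handles efficacy and safety differently within one sentence. For efficacy, "The disease-free survival (DFS) and overall survival (OS) were compared between the groups". For safety, "the adverse events (AE) in the SBRT group were recorded". It does not mention AEs in the surgery-alone group.

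The other relevant places are:

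- Protocol item 7: "The conventional open partial hepatectomy was applied in this study". This covers both arms, since randomization follows surgery and pathology.
- Protocol item 2: "Marginal resection was applied while tumor was adjacent to major vasculature or severe cirrhosis existed".
- Protocol item 9: "All the participants received follow-up every 3 months until recurrence or censored". Both arms therefore return on the same interval, but the item does not say that AEs are collected at these visits.
- SAP, Statistical analysis: "The comparison of clinical parameters between the two groups were conducted by" a list of standard tests. AEs are not mentioned.

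One part of the SAP was not available for review, so statements here about what is absent apply to the available text only.

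**The concern.** A count of AEs in one arm gives the incidence in that arm. It does not give the effect of treatment. SBRT is given one month after surgery, when events from the hepatectomy or the underlying liver disease can still occur, and the same background applies to the control arm. Randomization would let the background cancel in a between-arm comparison, but only if it is measured in both arms.

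What is at stake is the harm side of the comparison. Readers would see a DFS and OS difference beside an SBRT-only toxicity list, and could not tell how much of that list SBRT caused. The limit applies to non-fatal events, because deaths are counted in both arms through OS.

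**Working it through.** **No figure to reproduce.** The documents give no AE rate, effect size or power calculation. All AE counts, AE rates and DFS medians below are assumptions. Allocation is 1:1 (item 5). The n=76 in item 5 could be the total (38 per arm) or the SBRT arm (76 per arm), so both are shown.

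**Step 1: what one-arm data identify.** Let p1 and p0 be the AE risks with SBRT and with surgery alone. If p0 is never observed, it may lie anywhere from 0 to 1, so the difference p1 − p0 lies anywhere from p1 − 1 to p1.

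| Assumed p1 | Possible difference (points) |
|---|---|
| 10% | −90 to +10 |
| 20% | −80 to +20 |
| 30% | −70 to +30 |
| 40% | −60 to +40 |

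The range is 100 points wide at any sample size.

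**Step 2: the same SBRT result under different unseen controls.** With 38 per arm, take 11/38 = 28.9% in the SBRT arm (Wilson 95% CI 17 to 45). With 76 per arm, take 22/76, the same proportion. Differences have Newcombe 95% CIs.

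| Control count (38 per arm) | Difference | Control count (76 per arm) | Difference |
|---|---|---|---|
| 2/38 | 23.7 (6.7 to 39.9) | 4/76 | 23.7 (12.0 to 35.2) |
| 8/38 | 7.9 (−11.5 to 26.6) | 16/76 | 7.9 (−5.9 to 21.3) |
| 11/38 | 0 (−19.8 to 19.8) | 22/76 | 0 (−14.2 to 14.2) |

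The plan as written could not tell these rows apart.

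**Step 3: what recording in both arms would give.** The Wald 95% half-width is 1.96 × √[p1(1−p1)/n + p0(1−p0)/n]. For example, with p1 = 30%, p0 = 10% and n = 38, it is 1.96 × √[(0.21 + 0.09)/38] = 1.96 × 0.0889 = 17.4 points.

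| Assumed p1 / p0 | Half-width, 38 per arm | Half-width, 76 per arm |
|---|---|---|
| 10% / 5% | 11.8 | 8.3 |
| 20% / 10% | 15.9 | 11.2 |
| 30% / 10% | 17.4 | 12.3 |
| 40% / 20% | 20.1 | 14.2 |

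The full intervals are twice these: about 24 to 40 points wide at 38 per arm and 17 to 28 at 76 per arm.

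**Step 4: a caution for the repair.** Item 9 visits end at recurrence. If AEs were collected only at those visits and compared as crude proportions, the arm with longer DFS would be watched for longer. Assume the same constant AE hazard of 0.02 per month in both arms, exponential recurrence found at the next 3-monthly visit, a 36-month cut-off, and median DFS of 12 v 24 months. The share with any AE is the sum over visit times t of P(observation stops at t) × (1 − exp(−0.02t)).

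- Mean observation is 16.5 v 23.4 months, and the share with an AE is 26.3% v 35.3%. That is a false excess of 9.1 points before rounding (5.6 to 11.2 for hazards of 0.01 to 0.03).
- This depends on the hazard staying constant. If AEs are confined to the first 12, 6 or 3 months, the false excess falls to 2.0, 0.4 or 0.0 points.
- A 6-month window completed by everyone gives 1 − exp(−0.12) = 11.3% in both arms.

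Step 4 describes a possible repair. The current plan makes no such comparison.

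**The case against.** The strongest reply is that the trial does not set out to compare safety. The Objectives and Design paragraphs both state the aim as efficacy, DFS and OS are the compared outcomes, and AEs are listed separately as a record of the treated group. On that reading, one-arm toxicity reporting is a consistent design choice. This stands as far as it goes: it limits the weight of the point, and nothing here alters the DFS or OS result. It does not restore the lost information, since the Protocol itself names AEs as something to be recorded.

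A second reply is that the gain is modest. Under the assumed risks in step 3, power at two-sided 0.05 is 13%, 23%, 59% and 48% at 38 per arm, and 21%, 41%, 88% and 77% at 76 per arm. That also stands. The repair would give an estimate with an honest interval, often not a firm conclusion, but at present there is no estimate at all.

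A third reply is that control-arm events may have been noted at the 3-monthly visits, or that the unavailable part of the SAP provides for them. Either is possible. A reader might infer that events after surgery alone went unrecorded in practice, but the documents do not say so. They state a recording rule for one arm and are silent on the other. The SAP's general tests for clinical parameters do not fill the gap, because they need control-arm data.

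**Conclusion.** The point holds as a limit on the safety information. With AE recording provided for in the SBRT group alone, the trial can describe that group's AEs but cannot estimate the randomized difference in non-fatal AEs, nor separate SBRT effects from surgical and liver-disease events. The non-identification follows from the design and needs no assumed rates; the counts and interval widths are illustrations only. The meaning of n=76 does not change the conclusion.

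It is a cheap improvement, not a threat to the efficacy analysis. A reader might go further and infer that DFS is biased, because item 5 says "Participants in SBRT group would be sent to a separate team of radiologists who carried out the radiotherapy and follow-up survey" and item 6 says "blinding was not applied due to the SBRT procedure". The available text does not support that. The item 5 wording fits a survey after radiotherapy as well as it fits assessment of recurrence, no available text says who declares recurrence in either arm, and part of the SAP was not available.

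**What to change.** In Methods and item 9, state the following:

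> AEs are recorded and graded with the same scale in both arms, at the same contacts timed from surgery, from randomization to a fixed month X set by the sponsor, whether or not recurrence has occurred. The proportion with an AE by month X is compared between arms with the SAP's chi-square or Fisher's exact test and reported as a difference with a 95% CI.

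If AE visits must stop at recurrence, compare time to first AE instead, so that unequal observation is accounted for. If AEs after surgery alone were already being collected, a sentence saying so, with the scale and the window, would be enough.

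The cost is one more form in the control arm and some AE contacts after recurrence. The 3-monthly visits and the tests are already in the plan. The report should state that precision is limited, so that a wide interval is not read as evidence of equal safety.

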## Protocol

- 1. Adult patients diagnosed with hepatocellular carcinoma, suitable for partial hepatectomy were considered as potential candidates while the patients were referred to hospital (n=263).
- 2. In-hospital examination includes physical status, liver function and tumor stage. Patients with Child-Pugh A liver function, ECOG physical status 0/1, and BCLC stage 0/A were good candidates for surgical resection. These patients would be put forward to surgery and waiting for the postoperative pathological examination. Marginal resection was applied while tumor was adjacent to major vasculature or severe cirrhosis existed. We routinely mark the unsafe resection margin with silver clips for potential adjuvant postoperative therapy.
- 3. Once pathological examination proved micro-vascular invasion in paratumoral tissue, which meant a higher incidence of early recurrence for the patient, the patient would be considered as a candidate for enrollment.
- 4. The protocol and detail of the trial would be clearly explained to the patient and the written informed consent were collected if the patient agreed to be enrolled.
- 5. Randomization: Randomization was carried out using the random sequence method of EXCEL, keeping a 1:1 ratio in groups. Two nurses on daily duty accomplished the randomization and allocation work. Participants in SBRT group would be sent to a separate team of radiologists who carried out the radiotherapy and follow-up survey (n=76).
- 6. Concealment: Concealment was not attached in the SBRT group and blinding was not applied due to the SBRT procedure.
- 7. Surgery: The conventional open partial hepatectomy was applied in this study. After removal of the tumor, silver clips were imbedded to mark where resection

margin was narrow and absent. The marginal liver resection was defined as the minimal distance from tumor edge to the cut surface <5mm, regardless of the margin was positive or not.

- 8. Radiotherapy: SBRT was delivered by the CyberKnife® system (Accuracy Inc., Sunnyvale, CA, USA) with tumor tracking devices. All the patients received fiducial marker implantation in operation for the tumor tracking technique.
- 9. Follow-up: All the participants received follow-up every 3 months until recurrence or censored.

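### The plan does not establish that allocation was concealed: item 6 is ambiguous, list custody and the reveal step are not stated, and no analysis of the randomised set would address selective enrolment

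*Protocol*

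**What the plan says.** Protocol item 6, which has its own concealment label, reads: "Concealment was not attached in the SBRT group and blinding was not applied due to the SBRT procedure". Item 5 describes the mechanism: "Randomization was carried out using the random sequence method of EXCEL, keeping a 1:1 ratio in groups", and "Two nurses on daily duty accomplished the randomization and allocation work". Consent is the preceding step; under item 4, "the written informed consent were collected if the patient agreed to be enrolled". Item 5 closes with n=76, placed after a sentence about the SBRT group, so it could be the total or one arm. Item 1 counts patients at referral, who "were considered as potential candidates while the patients were referred to hospital (n=263").

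In the SAP, Statistical analysis, "The comparison of clinical parameters between the two groups were conducted" with standard two-sample tests. For the endpoints, "The DFS and OS were determined by the Kaplan-Meier method which was generated by the log-rank test". The Cox regression is directed at all BCLC 0/A patients operated on while recruitment was open, not at the randomised patients. Part of the SAP was not available, so any statement here that something is not described refers to the available text only.

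**The concern.** Concealment and blinding are different safeguards. Blinding hides the treatment after assignment, and radiotherapy against no radiotherapy makes that impractical. Concealment hides the next assignment until the patient is irrevocably enrolled, and it is feasible in any open-label trial. Item 6 puts both in one sentence and offers one reason, which can justify only the absence of blinding.

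In a single-centre, unblinded trial, random assignment is the main protection against confounding. It protects only if the person deciding on enrolment cannot know which arm comes next. If that person can know, a patient with a better outlook can be offered entry when SBRT is next, or one with a worse outlook when surgery alone is next. The DFS and OS comparison would then carry that difference.

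**Working it through.** **1. Readings of item 6.**
- If the SBRT procedure is offered as the reason for both halves of the sentence, the reason is invalid for concealment.
- If it applies to blinding only, no reason is given for leaving allocation unconcealed.
- If concealment means masking after assignment (the restriction to the SBRT group points that way, since allocation concealment precedes the existence of an arm), the available text says nothing about allocation concealment.

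No reading yields a described concealment procedure.

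**2. What item 5 adds.** It gives the sequence source, the ratio and who carried out the work. It does not give custody of the list, its visibility to recruiters, or the moment of reveal. Item 4 comes before item 5, but the order of a list is not a rule that eligibility and consent are recorded before the arm is known.

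**3. What the analysis could do about it.** The between-group comparison of clinical parameters may detect an imbalance in a recorded factor. The log-rank test does not adjust for one, and the Cox model targets a different population.

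**4. Illustration of size.** The plan gives no figure to reproduce. The sizes 38 or 76 per arm follow from the two readings of n=76, and alpha of 0.05 is the SAP's, taken here as two-sided. Everything else is assumed: no true effect; a prognostic factor in half of patients with hazard ratio (HR) 1.5, 2 or 3; median DFS 24 months; follow-up of 24 to 72 months, giving about 54 events in 76 patients (108 in 152); and k steered slots, all favouring SBRT.

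With N patients in total and n per arm, f = k/N. The expected poor-prognosis share is 0.5(1−f) on SBRT and 0.5(1+f) on surgery alone, so the gap is f. For k=15, N=76: f = 15/76 = 0.197, or 40% v 60%. For k=30, N=152, f is the same.

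Chance that a chi-square test flags the gap: z = f/√(0.5/n).
- 38 per arm: 0.197/0.1147 = 1.72; P(Z > 1.96−1.72) ≈ 41%.
- 76 per arm: 0.197/0.0811 = 2.43; P(Z > 1.96−2.43) ≈ 68%.

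Chance of a false SBRT benefit: with E events, the log-rank statistic shifts by about f × ln(HR) × √E/2. For k=15, N=76, HR 2: 0.197 × 0.693 × √54/2 = 0.50, and P(Z > 1.96−0.50) ≈ 7%.

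Simulated null trials (Monte Carlo standard error about 0.2 to 0.6 points) beside this approximation:

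| Per arm | Steered | False SBRT benefit, HR 1.5 / 2 / 3, simulated | Approximation | Flagged, chi-square | Flagged, Fisher |
|---|---|---|---|---|---|
| 38 | 0 | 2.7 / 2.8 / 2.4% | 2.5% | 5% | not run |
| 38 | 4 | 2.9–3.4 / 3.4–3.5 / 4.1% | 3.0 / 3.4 / 4.0% | 7% | 4% |
| 38 | 15 | about 5 / 7 / 11% | 4.8 / 7.3 / 12.2% | 40% | 30% |
| 76 | 8 | 3.3 / 3.8 / 5.0% | 3.2 / 3.8 / 4.9% | 8–9% | 6% |
| 76 | 30 | 6.4 / 10.1 / 18.1% | 6.1 / 10.6 / 20.2% | 68% | 62% |

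The approximation runs high at HR 3; the simulated values are the ones to use.

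**5. Why a screening count is informative.** If steering worked by passing over unsuitable patients, each steered slot would skip on average (1−0.5)/0.5 = 1 eligible patient. Fifteen steered slots imply about 15 skipped (90% range 7 to 25), enough to show in a count of eligible patients not randomised.

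**The case against.** The strongest reply is that item 6 admits nothing. Concealment cannot be missing in one arm only, so the sentence probably concerns masking. That stands: a reader might infer that allocation is known to have been open, and the documents do not support this. What remains is that concealment is not described.

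Second, two named staff did the work and consent is listed first. A reader might infer that these nurses recruited patients, or that arms were known in advance; neither is stated anywhere.

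Third, a reader might treat the candidates not randomised (263−76 = 187, or 263−152 = 111 if 76 is one arm) as an unexplained pool. They are not: the 263 are counted at referral, before staging and fitness (item 2), marginal resection (items 2 and 7), MVI on pathology (item 3) and consent (item 4). Many may never have been eligible. Only the count at each filter is missing.

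Fourth, the planned baseline comparison might be dismissed as useless. At 38 per arm it misses the 40% v 60% gap more often than it finds it; at 76 per arm it finds it about two times in three.

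Finally, the magnitude is wholly assumed. Light steering is close to simulation noise at HR 1.5, the larger figures need about 20% of slots steered in one direction, and the narrow entry population makes HR 3 the less likely end. That also stands, and it limits the severity. It does not close the gap in the text.

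**Conclusion.** The point holds as a gap in the plan: on any reading of item 6, the available text provides neither a concealment procedure nor a valid reason for its absence. Selective enrolment therefore cannot be excluded, and no planned analysis of the randomised set addresses it beyond a baseline comparison whose sensitivity depends on what n=76 means. The documents do not show that selection bias occurred.

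The conclusion rests on the wording of items 4 to 6 and of the SAP. The percentages show scale under assumed steering and are not estimates for this trial. Should-fix rather than must-fix: the remedy is cheap, but harm is not demonstrated, and if enrolment is complete only disclosure and analysis can change.

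**What to change.** 1. For any patient still to be randomised, keep the Excel 1:1 method. Have existing staff with no recruiting role hold the sequence in sequentially numbered opaque sealed envelopes or a locked file. Reveal each arm only after eligibility is confirmed, consent is signed and the patient is registered. Reword item 6 so that allocation concealment and blinding are separate statements.
2. For patients already randomised (the past tense and the counts suggest this may be all of them), state who held the list and when arms were revealed, and claim concealment only if that record supports it. State whether 76 is the total or one arm. Report counts at each filter (staging, marginal resection, MVI, consent), including eligible patients not randomised, with baseline balance by arm.
3. Add to the SAP a sensitivity Cox model for DFS and OS in the randomised set, with arm plus recorded baseline covariates. Item 2 already assesses candidates ("Patients with Child-Pugh A liver function, ECOG physical status 0/1, and BCLC stage 0/A were good candidates for surgical resection"), so BCLC 0 v A and ECOG 0 v 1 are examples. Label it post hoc if it is added after enrolment or data access.

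The cost is minor administrative work, a screening count and one extra model per endpoint, with no extra patients or procedures. The limit is that adjustment cannot remove selection on unrecorded factors, which is why the disclosure in step 2 is needed as well.

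### The only follow-up end rule in the available text stops at recurrence, yet overall survival is compared between arms; survival follow-up after recurrence and an OS censoring rule need to be stated

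*Protocol*

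**What the plan says.** The Methods paragraph at the start of the Protocol names two efficacy comparisons: "The disease-free survival (DFS) and overall survival (OS) were compared between the groups". The SAP, under Statistical analysis, treats both alike: "The DFS and OS were determined by the Kaplan-Meier method which was generated by the log-rank test". It also looks for "independent risk factors of DFS and OS in the entire group of BCLC 0/A patients receiving operation in the recruitment period", a wider group than the randomised patients.

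On the timing and end of follow-up, the available text has one rule, Protocol item 9: "All the participants received follow-up every 3 months until recurrence or censored". It does not name death, and it does not define censoring. The only other mention of follow-up is in item 5, which says who does it in one arm: "Participants in SBRT group would be sent to a separate team of radiologists who carried out the radiotherapy and follow-up survey (n=76".

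The available text gives no definition or time origin for OS, no data cut-off, no means of learning vital status after recurrence, and no OS censoring rule. One part of the SAP was not available for this review and may contain some of these.

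**The concern.** Recurrence is a DFS event, so a schedule that ends there loses nothing for DFS. For OS it stops observation before most of the deaths that matter. Item 3 makes this pressing: patients become candidates because of microvascular invasion, "which meant a higher incidence of early recurrence for the patient".

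If item 9 also governs OS, a patient who recurs leaves the risk set at that visit. Two things follow whenever recurrence raises mortality. First, the censoring is informative and the OS curves are biased upward. Second, if SBRT prolongs life by preventing recurrence, the deaths it prevents are the ones never recorded, so the OS comparison cannot show the benefit.

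If some recurred patients are followed informally, the bias shrinks, but a second risk appears. Item 5 gives follow-up of the SBRT arm to a separate team, so the share followed could differ between arms.

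**Working it through.** The plan states no event rate, effect size, power or follow-up length, so there is no figure to reproduce. What follows shows scale only. **Every rate is an assumption; none is in the documents.**

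**Assumed inputs.** Horizon T = 60 months and exponential times. Median time to recurrence is 18, 24 or 36 months. Median survival after recurrence is 18, 24 or 30 months. Death without recurrence is 1, 2 or 5% per year. The last range is wide because item 2 mentions both Child-Pugh A function ("Patients with Child-Pugh A liver function, ECOG physical status 0/1, and BCLC stage 0/A were good candidates for surgical resection") and severe cirrhosis ("Marginal resection was applied while tumor was adjacent to major vasculature or severe cirrhosis existed"). This gives 3 x 3 x 3 = 27 scenarios.

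**Model.** Let r = ln2/(median time to recurrence), p = ln2/(median survival after recurrence), q = yearly rate of death without recurrence/12, and a = r + q.

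- Alive without recurrence: S0(t) = exp(-at).
- Alive after recurrence: S1(t) = r[exp(-pt) - exp(-at)]/(a - p).
- True OS(t) = S0(t) + S1(t).
- Deaths without recurrence: d0 = (q/a)(1 - exp(-aT)). Deaths after recurrence: d1 = 1 - OS(T) - d0.
- A random share c of recurred patients is followed to death or T; the rest are censored at recurrence. Share of deaths seen = (d0 + c d1)/(d0 + d1).
- Kaplan-Meier limit = exp(-∫[qS0 + cpS1]/[S0 + cS1] dt), from 0 to T.

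**Worked example: 24 months, 30 months, 2% per year, 76 patients.** r = 0.02888, p = 0.02310, q = 0.00167, a = 0.03055. True 5-year OS = 0.51. d0 = 0.0458 and d1 = 0.4448, so there are 76 x 0.4906 = 37.3 deaths.

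With c = 0, only 76 x 0.0458 = 3.5 deaths are seen and the Kaplan-Meier limit is exp(-60q) = exp(-0.10) = 0.90. That expression does not contain r. Halving the recurrence rate in one arm therefore changes nothing in the estimate, although true 5-year OS rises from 0.51 to 0.65.

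| Share followed, c | Deaths seen (of 37.3) | Estimated OS (true 0.51) | Estimated difference, recurrence rate halved (true 14.0 points) |
|---|---|---|---|
| 0 | 3.5 | 0.90 | 0 |
| 0.25 | 11.9 | 0.71 | 10.2 |
| 0.50 | 20.4 | 0.61 | 13.2 |
| 0.75 | 28.8 | 0.55 | 14.1 |
| 0.90 | 33.9 | 0.52 | 14.1 |

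**All 27 scenarios (true 5-year OS 0.28-0.62).**

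| Share followed | Deaths seen | OS overstated, points | Share of true difference kept |
|---|---|---|---|
| 0 (worst case) | 3-29% | 25-63 | 0% |
| 25% | 27-46% | 15-28 | 53-97% |
| 50% | 51-64% | 7-15 | 80-111% |
| 75% | 76-82% | 3-6 | 93-107% |
| 90% | 90-93% | 1-2 | 98-103% |

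**Test size.** With no SBRT effect and equal ascertainment in both arms, simulated two-sided log-rank rejection at 0.05 is 4.5-5.7% for c from 0.5 to 1. At c = 0 it is 0.6-5.3% with 38 per arm and 2.2-5.5% with 76 per arm. So there is no inflation. With 90% followed in one arm and 50% in the other (worked-example rates, no effect), rejection is about 10% with 38 per arm and about 17% with 76 per arm; repeat runs differ by up to about a point. Both sizes are shown because item 5 does not make clear whether 76 is the randomised total or the SBRT arm.

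**Power.** With the recurrence rate halved and full survival follow-up, OS power is 13-42% (38 per arm) or 23-72% (76 per arm). At c = 0 it is 2-5% or 3-5%.

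**The case against.** The strongest reply is that item 9 is a recurrence-surveillance schedule and was never meant to govern OS. It ends at a DFS event, which fits that reading. The SAP's OS risk-factor analysis covers all operated BCLC 0/A patients, some of whom were not randomised and so are not item 9's participants. Their survival data must come from somewhere else, which suggests that another source of vital status exists. The part of the SAP that was not available may also define OS and its censoring.

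This stands as far as it goes. A reader might infer from item 9 that OS was in fact censored at recurrence and that deaths were lost. The documents do not support that. What does not follow is that the gap is closed. Nothing available says that another source covers randomised patients after recurrence, in both arms, to the same date. A SAP definition would still need data that item 9, as worded, does not collect.

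A second objection is that the sizes rest on assumed rates and are driven almost entirely by the unknown share followed. That is correct. The 0% row is a bound, not a forecast, and at 90% the error is minor. The intermediate rows assume that those followed are a random subset, equally in both arms, which nothing in the text secures.

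A reader might also infer that the OS test is invalid. With equal ascertainment it is not inflated. A separate follow-up team in the SBRT arm makes unequal ascertainment possible; it does not demonstrate it.

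**Conclusion.** The point holds in conditional form. The one available rule on the end of follow-up fits DFS and does not fit OS, and no available text supplies a separate OS rule. Read literally, it produces OS curves that are too high and conceals any benefit acting through recurrence. Read as surveillance only, it shows no bias, but it leaves OS without a stated follow-up or censoring rule.

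The consequence ranges from minor, if nearly all recurred patients are followed, to severe, if none are. The documents do not say where the trial lies in that range. Unequal follow-up between arms is a further risk to test size. These sizes assume constant hazards, a 60-month horizon and the rates listed above. OS power is limited even with complete follow-up, so the gain from correction is mainly an unbiased OS estimate. The DFS comparison is not affected by this point.

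**What to change.** 1. In item 9, limit the stop at recurrence to recurrence surveillance for DFS.
2. Obtain vital status for every randomised patient, in both arms and by the same method, to one common cut-off date regardless of recurrence. If follow-up has ended, as the largely past-tense text suggests, do this by a single retrospective retrieval. Three-monthly contact after recurrence is not needed for an unbiased OS estimate.
3. State in the SAP, or reconcile with the part not available here: *OS is the time from randomisation to death from any cause, censored only at the last date known alive or the common cut-off, and never at recurrence.*
4. Report, by arm, the number of patients whose vital status at the cut-off is unknown.

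The cost is two text changes and one vital-status check per recurred patient. Recurrence by 60 months is (r/a)(1 - exp(-aT)) = 62-89% under the assumed rates, so 76 x 0.62 = 47 to about 67 checks for 76 patients. The count is lower if SBRT reduces recurrence, and double if 76 is one arm. Some patients are likely to remain unknown, which is why item 4 is needed. No new patients or procedures are required.
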